**t tests - Means: Difference between two independent means (two groups)**

**Analysis:** A priori: Compute required sample size

**Input:**

Tail(s)	= Two
Effect size d	= 0.6666667
$\alpha$ err prob	= 0.05
Power (1- $\beta$ err prob)	= 0.8
Allocation ratio N2/N1	= 1

**Output:**

Noncentrality parameter $\delta$	= 2.8674419
Critical t	= 1.9934636
Df	= 72
Sample size group 1	= 37
Sample size group 2	= 37

Sample size was determined using G\*Power version 3.1.9.2 software. Using preliminary data, we estimate that we will need 37 subjects in each group (N=74) to have sufficient power (80%) at alpha=0.05 to test the hypothesis of a difference in mean change in IS for the two groups. To account for attrition due to withdrawals, we intend to enroll 50 patients per group. In the event that no withdrawals occur, enrolling 100 subjects (50 in each group) will give 91% power to distinguish between the two groups.

**t tests - Means: Difference between two independent means (two groups)**

[figure not shown]
**Analysis:** Post hoc: Compute achieved power

**Input:**

Tail(s)	= Two
Effect size d	= 0.6666667

$\alpha$ err prob	= 0.05
Sample size group 1	= 50
Sample size group 2	= 50
Output: Noncentrality parameter $\delta$	= 3.3333335
Critical t	= 1.9844675
Df	= 98
Power (1- $\beta$ err prob)	= 0.9099634

Baseline clinical and demographic factors for each group will be collected. Categorical data will be compared across the two groups with Chi-square tests of homogeneity and continuous data will be compared with t-tests for means. Covariates determined to be associated with IS measurement will be assessed for inclusion in a multivariate linear model.

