## 2.0 Background

Enhanced recovery after surgery (ERAS) protocols are evidence based care improvement processes for surgical subjects. Implementation of ERAS programs for perioperative management after surgery has resulted in major improvements in clinical outcomes and costs, making ERAS an important example of value-based care applied to surgery.

Currently, MUSC has existing ERAS protocols in place for hepatobiliary and colorectal surgeries. These uniform ERAS protocols cover fluid intake, hydration, anti-emetics, pain control, and several other considerations. Ventilator management is not standardized in ERAS protocol and is left to the discretion of the anesthetic practitioner. Numerous studies have shown improvement in perioperative surgical outcomes with the use of lung protective [ventilator] strategies. We are trying to prove that the addition of specific lung protective strategies to existing ERAS protocols can further improve subject post-operative lung function as measured by improved mean incentive spirometry inspiratory capacity readings compared to the controls.

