## 5.0 Inclusion and Exclusion Criteria/ Study Population

### Inclusion Criteria

- All subjects going for scheduled colorectal or hepatobiliary surgery at the MUSC ART hospital who would normally be utilizing the existing ERAS protocols
- English speaking
- Able to give informed consent
- Ages 18 years and older

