## 10.0 Study Design / Methods

- After obtaining informed consent, the subjects will be provided with an incentive spirometer. They will be educated in its use and will then proceed to take three separate maximum exertion inspiratory capacity breaths. All three measurements will be recorded and the subjects will then be randomized to the control or intervention group.
- They will proceed to the operating room where the existing baseline ERAS protocol for colorectal or hepatobiliary surgery will be implemented during their surgery. In addition to the existing protocols, the five lung protective strategies listed above will also be implemented throughout the course of the surgery for the intervention group.
- In the PACU, the subjects will be asked at the 30 minute, 1 hour, and 2 hour marks (time zero will be arrival to PACU) to once more take three separate maximum exertion inspiratory capacity breaths and all three measurements will be recorded.
- If the subjects are unable or unwilling to comply, this will be documented as well and re-attempted at the next scheduled study documentation milestone.
- The information that will be pulled from the subject's medical record will include age, gender, weight, height, BMI, O2 saturation, average intra-op tidal volume, and the absence or presence of supplemental O2 use.
- The data collected for the intervention subjects who will have the standardized lung protective strategies applied will then be compared to the control subjects who underwent the same surgeries and had the same colorectal and hepatobiliary protocols implemented, but without the use of standardized lung protective strategies.

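### The adjusted model selects covariates by observed association and does not bar post-randomisation variables, while planned surgical approach and planned block are not listed as baseline data (minor)

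*Combined protocol and SAP*

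**What the plan says.** The endpoint depends on effort. At 30 minutes, 1 hour and 2 hours after arrival in the recovery unit, patients are asked "to once more take three separate maximum exertion inspiratory capacity breaths and all three measurements will be recorded" (section 10.0). The same three breaths are taken before surgery, after which "the subjects will then be randomized to the control or intervention group". No stratification is stated.

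The only itemised list of chart data, also in section 10.0, is "age, gender, weight, height, BMI, O2 saturation, average intra-op tidal volume, and the absence or presence of supplemental O2 use". Section 11.0 adds oxygen saturation and supplemental oxygen in the recovery unit as secondary outcomes.

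The last paragraph of section 11.0 opens with "Baseline clinical and demographic factors for each group will be collected", without naming any. It closes with the modelling sentence: "Covariates determined to be associated with IS measurement will be assessed for inclusion in a multivariate linear model". The primary analysis, stated earlier in section 11.0, is a two-sided test of mean change in incentive spirometry (IS). The linear model is therefore additional to it.

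The inclusion criteria in section 5.0 admit "All subjects going for scheduled colorectal or hepatobiliary surgery at the MUSC ART hospital who would normally be utilizing the existing ERAS protocols", with no restriction by approach. On analgesia, section 2.0 says only this: "These uniform ERAS protocols cover fluid intake, hydration, anti-emetics, pain control, and several other considerations".

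**The concern.** Two weaknesses meet in the modelling sentence.

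The first is how covariates are chosen. The model's content depends on which variables turn out to be associated with IS in the trial data, so it cannot be known in advance. Nothing confines the choice to variables fixed before randomisation. Tidal volume is one of the things the intervention standardises (section 3.0), so adjusting for it would remove part of the effect under study. Supplemental oxygen after surgery is itself an outcome that may respond to the allocated arm.

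The second is what is available to choose from. How deeply a patient can inspire soon after abdominal surgery plausibly depends on the incision and on whether a block is in place. The planned versions of both are known before randomisation and would be legitimate covariates. Neither is named in the documents. A model cannot use what was not recorded, and a baseline table cannot show an imbalance in it.

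At stake are the credibility of the adjusted result, some precision, and the ability to see a chance imbalance.

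**Working it through.** **The plan's own figures.** Inputs from section 11.0: d = 0.6666667, two-sided alpha 0.05, power 0.80, equal arms. The two-sample t test with the noncentral t distribution gives 37 per group (power 0.8076, noncentrality 2.8674, critical t 1.9935). With 50 per group, power is 0.9100 (noncentrality 3.3333, critical t 1.9845). Both stated results reproduce.

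The same section assumes mean changes of about 1000 and 800 mL and a shared SD of 350 mL. That gives d = 200/350 = 0.571. The d that was entered matches 200/300. This is a separate matter, but it sets the starting point here: at SD 350 mL, power is 0.808 with 50 per arm and 0.679 with 37. There is little precision to spare.

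**Which variables are candidates.**

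| Variable | Where it stands | Fixed before randomisation? |
|---|---|---|
| Age, gender, weight, height, BMI | section 10.0 list | yes |
| Baseline IS | three breaths, section 10.0 | yes |
| Average intra-operative tidal volume | section 10.0 list; set by the intervention, section 3.0 | no |
| Supplemental oxygen | section 10.0 list; secondary outcome, section 11.0 | no, for values after surgery |
| Planned approach, planned block | not listed | yes, if recorded |
| Pain or opioid at the reading | not listed | no |

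**Size of the precision loss.** The documents give no effect size for approach or block. Assumption: one binary factor shifts the IS change by b = 100 to 300 mL and is present in a proportion p = 0.3 to 0.5 of patients. Then:

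- share of variance R² = p(1−p)b²/350²
- residual SD = 350·√(1−R²)
- SE of the arm difference at 50 per arm = residual SD·√(2/50)

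Power is for a 200 mL difference.

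| b (mL) | p | R² | Residual SD (mL) | SE (mL) | Power, 50 per arm | Power, 37 per arm |
|---|---|---|---|---|---|---|
| no adjustment | – | 0 | 350.0 | 70.0 | 0.808 | 0.679 |
| 100 | 0.3 | 2100/122500 = 0.017 | 347.0 | 69.4 | 0.814 | 0.686 |
| 200 | 0.5 | 10000/122500 = 0.082 | 335.4 | 67.1 | 0.839 | 0.716 |
| 300 | 0.5 | 22500/122500 = 0.184 | 316.2 | 63.2 | 0.879 | 0.765 |

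These powers use 98 degrees of freedom at 50 per arm. Spending three on covariates leaves 95, and the first and last rows stay at 0.814 and 0.879.

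**Size of a chance imbalance.** The SD of the shift it causes in the arm difference is b·√(2p(1−p)/50):

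- b = 100, p = 0.3: 100·√0.0084 = 9.2 mL
- b = 300, p = 0.5: 300·√0.01 = 30.0 mL

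This is not error on top of the SE. It is already part of the 70 mL: √(70² − 30²) = 63.2 mL, the adjusted SE in the last row.

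**The case against.** Most of the case on the other side stands, and it limits the point.

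- **The items may be collected after all.** A reader might infer that approach and block will not be recorded. The documents do not show that. Section 11.0 promises baseline clinical factors without defining them, and these could include both. The supportable statement is that they are not listed.
- **Randomisation protects the primary comparison.** A reader might infer confounding by analgesia or incision. Allocation is random and the primary test is unadjusted, so leaving these variables out does not bias it.
- **Pain at the reading is no loss to the model.** A reader might want it as a covariate. It is measured after randomisation and may respond to the allocated arm, so it does not belong in a model for the treatment effect. The same holds for analgesia actually given and for the approach after a conversion.
- **Analgesia may vary little.** Pain control falls under protocols described as uniform and used in both arms. But section 2.0 neither describes the technique nor says that it is the same for both types of surgery, and it does not touch incision type.
- **Tidal volume and oxygen may not be meant as covariates.** The paragraph opens with baseline factors, which may be all that is intended. But the modelling sentence carries no such limit, and section 10.0 lists these variables alongside age and BMI.

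**Conclusion.** The point holds as a minor one. Planned approach and planned block are not listed, the adjusted model is chosen by observed association, and nothing bars variables affected by treatment. The clearest defect is the last: an adjusted estimate that conditions on tidal volume or postoperative oxygen use could not be read as the effect of the intervention.

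The precision loss is small to moderate, and its size rests wholly on the assumed 100 to 300 mL shift at 30 to 50% prevalence. On that range, power at SD 350 mL and 50 per arm moves from 0.81 to between 0.81 and 0.88. A reader might call approach and block strong determinants. The documents give no figure to support that, and the low end of the range is close to nothing.

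The primary result is not put in doubt.

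**What to change.** In section 10.0, add planned approach (open or minimally invasive) and planned neuraxial or regional block (yes or no), both recorded before randomisation. The chart review for eligibility in section 8.0 is a natural time to do it.

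In section 11.0, replace the selection sentence with a pre-named linear model for the change in IS, containing arm, baseline IS (already measured), planned approach and planned block. State that variables arising after randomisation, including tidal volume, supplemental oxygen, pain and opioid use, are not used as adjusters.

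Optionally, report routine chart pain scores and recovery-unit opioid by arm, descriptively only. They may help in reading failed attempts, but they cannot separate effort from lung function.

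The cost is two chart fields, a rewritten sentence and about three of 98 degrees of freedom. No new procedure is needed. Any patient randomised before the change would need the planned values taken from preoperative notes.

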## 12.0 Provisions to Monitor the Data to Ensure the Safety of Subjects (if applicable)

Data and safety monitoring will be performed by the research study committee in the Department of Anesthesia and Perioperative Medicine on an annual basis. The committee is comprised of several attending anesthesiologists, an emeritus dean of medicine and a biostatistician. Any adverse events will be reported to MUSC's IRB per protocol and will be evaluated by the committee.

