## 4.0 Study Endpoints (if applicable)

- The end-point of the study will be completion of the 3rd incentive spirometry breath measurement at the 2 hour mark, whether it be in PACU or on the inpatient floor
- Study termination would include need for post-operative mechanical ventilation, need for post-op BIPAP/CPAP, admission to ICU, or inability to adhere to lung protective interventions due to subject intolerance.

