## 6.0 Number of Subjects

- This study will include 100 subjects in order to detect a 20% difference in the anticipated decrease in incentive spirometry inspiratory capacity breaths for the control and intervention groups.

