## 14.0 Withdrawal of Subjects (if applicable)

- Participants will be withdrawn from the study if they expire intraoperatively, require post-op mechanical ventilation, require immediate ICU admission, require post-op BIPAP or CPAP use, or intra-operatively do not meet ventilation goals within the prescribed ventilator guidelines (likely due to intrinsic pathology).

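### Death, ventilation, ICU admission and BIPAP/CPAP take subjects out of the study but are never counted by arm, and the scheduled safety review does not fill the gap

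*Combined protocol and SAP*

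**What the plan says.** Section 14.0 (Withdrawal of Subjects) states: "Participants will be withdrawn from the study if they expire intraoperatively, require post-op mechanical ventilation, require immediate ICU admission, require post-op BIPAP or CPAP use". It adds subjects whose ventilation goals cannot be met within the prescribed guidelines. Section 4.0 (Study Endpoints) gives a similar list as grounds for termination, without death and with intolerance of the lung protective measures added.

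Section 11.0 (Data Management) names inspiratory capacity as the primary outcome. The secondary outcomes are SpO2, its trend, and use of supplemental oxygen. None of the events in sections 4.0 or 14.0 appears there.

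On oversight, section 12.0 says: "Data and safety monitoring will be performed by the research study committee in the Department of Anesthesia and Perioperative Medicine on an annual basis". It continues: "Any adverse events will be reported to MUSC's IRB per protocol and will be evaluated by the committee". It does not define an adverse event, set a timeline, specify what the committee receives, or link a review to the number enrolled.

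Section 6.0 fixes the size: "This study will include 100 subjects". A subject's participation ends with the "incentive spirometry breath measurement at the 2 hour mark, whether it be in PACU or on the inpatient floor", and section 10.0 specifies that "time zero will be arrival to PACU".

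**The concern.** The intervention is a ventilator strategy. Post-operative ventilation, BIPAP/CPAP and ICU admission are therefore among the events that bear most directly on whether it helps or harms. The plan uses them to take subjects out and then names no analysis of them. The SpO2 and oxygen outcomes may not capture them, because the affected subjects have left the study.

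Two exit reasons can also fall unevenly by design. Intolerance of the lung protective measures, and failure to meet prescribed ventilation goals, mainly concern the arm in which ventilation is standardised. Without a by-arm count, a reader of the results cannot tell whether the two groups measured at two hours are still comparable, or whether one arm lost more of its sickest subjects.

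The review schedule adds to this. Exposure and follow-up are over on the day of surgery, so safety information accumulates as fast as subjects enrol, while the scheduled review follows the calendar.

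**Working it through.** **1. Where each event appears**

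| Event | Exit reason | Outcome in 11.0 | By-arm count required |
|---|---|---|---|
| Intra-operative death | 14.0 | No | Nowhere |
| Post-operative mechanical ventilation | 4.0 and 14.0 | No | Nowhere |
| ICU admission | 4.0 and 14.0 (immediate) | No | Nowhere |
| BIPAP/CPAP | 4.0 and 14.0 | No | Nowhere |
| Intolerance of the lung protective measures | 4.0 | No | Nowhere |
| Ventilation goals not met | 14.0 | No | Nowhere |

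Section 12.0 reaches these events only if someone classes them as adverse events, and it does not say that they are.

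**2. How many exits the plan allows for**

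The plan's own figures come first. A two-sided two-sample t-test with d = 0.6666667 and alpha 0.05 gives 37 per group for 80% power (recomputed power 0.808, noncentrality 2.867). At 50 per group, power is 0.910. Both agree with section 11.0.

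Allowance for withdrawals = 100 − 74 = 26 subjects, or 26% of those enrolled. Not all need be serious events, but section 14.0 puts serious events among the reasons.

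**3. Whether there would be anything to count**

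The documents give no event rates, so a range is assumed. The chance of at least one event among the 50 intervention subjects is 1 − (1 − p)^50:

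- p = 1%: 39%
- p = 2%: 64%
- p = 5%: 92%

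**4. How many subjects precede a first annual review**

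Accrual and study duration are not stated. Assume the first review falls 12 months after the first enrolment. Subjects treated by then = min(100, 12 × monthly accrual):

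| Assumed accrual per month | Treated before the month-12 review |
|---|---|
| 2 | 24 |
| 4 | 48 |
| 6 | 72 |
| 8 | 96 |
| 8.3 or more | about 100 (all) |

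More than half requires accrual above 50/12 ≈ 4.2 per month. All requires about 100/12 ≈ 8.3 per month.

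**5. What a by-arm look could detect**

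This is the chance that a two-sided Fisher exact test at 0.05 shows an intervention-arm excess, with assumed event rates:

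| Control v intervention | 12 per arm | 25 per arm | 50 per arm |
|---|---|---|---|
| 5% v 15% | 1% | 7% | 24% |
| 5% v 20% | 4% | 20% | 51% |

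With no control events, significance needs 5 intervention events at 12 per arm and 6 at 25 per arm. Interim counts therefore give visibility but are not a useful formal test.

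**The case against.** The strongest reply is that section 12.0 already covers these events. Any adverse event goes to the IRB and is evaluated by the committee, and the text does not confine that evaluation to the annual meeting. An intra-operative death or unplanned ventilation would ordinarily be taken as an adverse event. This stands against a reading that a reader might infer, namely that the gravest events are recorded as exit reasons and nothing more. The documents do not support that, because a reporting route exists. What the route lacks is a statement that these exits fall within it, a timeline, and any count by arm. Such events can also follow major abdominal surgery without the intervention, so individual reports do not show whether one arm has more of them.

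A second tempting reading is that most or all subjects will be treated before anyone looks. That depends on accrual the documents do not give, and on when the annual cycle starts, which is also unstated. At 2 per month the first annual review comes after 24 subjects.

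Third, frequent looks would seldom reveal an excess, as step 5 shows. That stands too, and it is why a fixed short interval such as every 25 subjects is not pressed here.

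Finally, this is a single-centre study that excludes advanced lung disease and home oxygen, and its committee includes anesthesiologists and a biostatistician. No passage contradicts annual review, so the schedule alone is a design choice rather than an error.

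**Conclusion.** The gap in by-arm reporting is real and holds at any accrual rate. The plan removes subjects for its most serious respiratory and critical-care events, allows for up to 26 losses in 100, and requires no comparison of those events between arms. A favourable inspiratory-capacity result could therefore be published with nothing to show whether serious events were balanced.

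The timing of review is a secondary and conditional matter. The first annual look could follow anything from 24 subjects to all 100 over the assumed range of 2 to about 8.3 per month. This assumes a first review 12 months after enrolment begins.

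The conclusion does not rest on the assumed event rates. They serve only to show that there may well be events to count and that formal testing of them would have little power.

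**What to change.** - **Section 11.0:** add each event named in sections 4.0 and 14.0 as a safety outcome, counted by arm for all randomised subjects, including those withdrawn.
- **Section 12.0:** state that these events count as adverse events, and that the committee receives the cumulative counts by arm at each review.
- **Optional, section 12.0:** add at least one review tied to enrolment, for example at 50 subjects, alongside the annual one. Describe its purpose as visibility of the counts, since it has little power to detect an excess.

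The cost is one extra table, built from information the exits already generate, and slightly more committee preparation. The sample size, primary analysis and treatment rules are unchanged.

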## 14.0 Withdrawal of Subjects (if applicable)

- Participants will be withdrawn from the study if they expire intraoperatively, require post-op mechanical ventilation, require immediate ICU admission, require post-op BIPAP or CPAP use, or intra-operatively do not meet ventilation goals within the prescribed ventilator guidelines (likely due to intrinsic pathology).

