## 11.0 Data Management

- The primary outcome of interest is the inspiratory capacity obtained in the PACU via the incentive spirometer.
- The secondary outcomes that will be observed are the numerical value for SPO2, SPO2 trend, and use or lack thereof of supplemental O2 in PACU in 15 minute intervals or up to two hours after arrival there.

- Our primary hypothesis is that subjects that will have lung protective strategies employed on them will have 20% superior mean inspiratory capacity breaths via incentive spirometry compared to the non-intervention controls.
- Only IRB approved study team members will have access to data. Each study subject will be given a study ID number that will be used to identify them throughout the study. All study staff will have their CITI certification and receive protocol training. All data will be kept on a password protected MUSC server and in a redcap database. All paper documents will be kept in a locked office, in a locked cabinet that only IRB study team members have access to.
- Our primary hypothesis is that use of lung protection protocol will result in smaller change in lung function, measured by Incentive Spirometry (IS).

$H_0$ : change in ISI ≠ change in ISC

$H_A$ : change in ISI < change in ISC

The primary analysis will be a two-sided test of mean change in IS after surgery compared to pre-surgery IS.

Based on data from a study of 19 people undergoing lobectomy {Bastin, 1997 #14268}, we assume that the IS before surgery is 2642 mL (se=140; std=610). If the control group IS decreases by 40%, the mean change in the control group will be ~1000 mL (std dev=308). Assuming the intervention group IS decreases by 30%, the mean change in the intervention group will be ~800 mL. Assume shared std dev=350.

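### Randomised patients are withdrawn for later events, one of which by inference can arise only in the intervention arm, and nothing keeps them in the primary test

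*Combined protocol and SAP*

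**What the plan says.** Section 10.0 places randomisation after baseline spirometry and before the operating room: "All three measurements will be recorded and the subjects will then be randomized to the control or intervention group".

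Section 14.0 then lists reasons for withdrawal from the study, all of which follow randomisation. They are intraoperative death, patients who "require post-op mechanical ventilation, require immediate ICU admission, require post-op BIPAP or CPAP use", and patients who "or intra-operatively do not meet ventilation goals within the prescribed ventilator guidelines (likely due to intrinsic pathology". Section 4.0 has a similar list under study termination, ending with "inability to adhere to lung protective interventions due to subject intolerance".

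On ventilation in the control arm, Section 2.0 says: "Ventilator management is not standardized in ERAS protocol and is left to the discretion of the anesthetic practitioner". Section 3.0 confirms that controls have no standardised lung protective strategies.

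On the analysis, Section 11.0 says: "The primary analysis will be a two-sided test of mean change in IS after surgery compared to pre-surgery IS". It names no analysis set. It treats withdrawals as attrition and raises enrolment from 37 to 50 per group to allow for them. Section 10.0 has a rule for missed spirometry ("this will be documented as well and re-attempted at the next scheduled study documentation milestone"), but it is written for patients unable or unwilling to do the breaths, not for withdrawn patients.

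**The concern.** Randomisation makes the two groups comparable only if the groups analysed are the groups randomised. Here a patient can leave after randomisation because the assigned ventilation could not be delivered. Section 14.0 itself attributes this to probable underlying pathology, and the outcome is lung function. A similar patient in the control arm has no prescribed ventilation goal to miss, so that patient stays in and is not identified.

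If withdrawn intervention patients would have lost more IS than the others, removing them favours the intervention. If they would have lost fewer mL, removing them counts against it. The remaining reasons (ventilation, ICU, BIPAP/CPAP) can arise in either arm, but treatment might affect them, so losses there can also be unequal.

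Many of these outcomes need not be lost. A patient whose ventilation goals were not met may well be able to perform spirometry in PACU. Once the measurement has not been taken, no analysis can recover it.

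**Working it through.** **1. The plan's own figures.** Two-sample t-test, two-sided alpha 0.05, d = 0.6667 (Section 11.0). With 37 per group the noncentrality is 0.6667 × √(37/2) = 2.867, the critical t is 1.993 and power is 80.8%; 36 per group gives 79.7%. With 50 per group the noncentrality is 3.333 and power is 91.0%. Both stated figures reproduce.

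**2. What the extra enrolment protects.** If 13 of 50 intervention patients and no controls were lost, power at d = 0.6667 for 50 against 37 would still be 86%. The extra patients protect power. They do nothing about who is missing.

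**3. Is one reason arm-specific?** Section 14.0 refers to prescribed ventilator guidelines. Only Section 3.0 prescribes any, and only for the intervention arm; Section 2.0 leaves ventilation otherwise to the practitioner. The adherence wording in Section 4.0, which may be the same rule in other words, points the same way. This is an inference, because no arm is named.

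**4. Size, as an illustration.** From the plan: SD 350 mL, 50 per arm, target difference 1000 − 800 = 200 mL. Assumed: no true effect, a share q withdrawn from the intervention arm only, and correlation r between the loss in IS and a normal latent tendency to be withdrawn. With z the upper-q normal quantile and φ the normal density:

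shift = r × SD × φ(z) / (1 − q); gap between withdrawn and retained = shift / q.

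Example, q = 0.10, r = 0.6: 0.6 × 350 × 0.1755 / 0.90 = 40.9 mL; gap = 40.9 / 0.10 = 409 mL.

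| q | φ(z) | shift, r = 0.6 | share of 200 mL | gap | type I error, r = 0.6 | shift, r = 0.3 | type I error, r = 0.3 |
|---|---|---|---|---|---|---|---|
| 2% | 0.0484 | 10 mL | 5% | 519 mL | about 5% | 5 mL | about 5% |
| 5% | 0.1031 | 23 mL | 11% | 456 mL | about 6% | 11 mL | about 5% |
| 10% | 0.1755 | 41 mL | 20% | 409 mL | about 9% | 20 mL | about 6% |
| 20% | 0.2800 | 74 mL | 37% | 367 mL | about 17% | 37 mL | about 8% |

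Type I error is from simulation of the two-sided pooled t-test. With r > 0 the shift favours the intervention; with r < 0 it reverses; with r = 0 it vanishes. An equal share withdrawn from the control arm with the same gap would cancel it.

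**5. Cost of keeping non-adherent patients.** If a share q of intervention patients gain nothing, the expected difference is 200 × (1 − q): 190, 180 or 160 mL for q = 5%, 10% or 20%. The fair comparator is the current rule with those patients removed, 50 against 50 × (1 − q), and the full 200 mL retained without bias. SD 300 is the value implied by d = 0.6667 (200 / 0.6667); SD 350 is the value in the text.

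| q | SD 300: kept | SD 300: current rule | SD 350: kept | SD 350: current rule |
|---|---|---|---|---|
| 5% | 88% | 90% | 77% | 80% |
| 10% | 84% | 89% | 72% | 79% |
| 20% | 75% | 87% | 62% | 76% |

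**The case against.** The strongest reply is that the arm-specific reason may hardly ever occur. Section 3.0 sets an approximate tidal volume and allows PEEP and FIO2 to be titrated, and the exclusion criteria already remove several severe lung conditions and home oxygen. At 2% withdrawn (1 patient in 50) the shift is 10 mL even at r = 0.6, which is negligible against 200 mL. The larger figures need high withdrawal, no control losses and a gap of more than one SD, none of which the documents support. All of this stands. It limits the severity, but it does not justify a rule that discards outcomes that could be measured.

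Three stronger readings are tempting, and the documents do not support them.

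- *The plan specifies an analysis that excludes withdrawn patients.* It does not. Exclusion is inferred from withdrawal from the study, the attrition allowance and the absence of any rule to the contrary. Section 10.0 says "The data collected for the intervention subjects who will have the standardized lung protective strategies applied will then be compared to the control subjects", which is an ordinary description of two arms and defines no analysis set.
- *The result will be biased in favour of the intervention.* The pathology remark makes that direction plausible, but no withdrawal rate, arm split or link to outcome is given.
- *The sponsor expects 26% withdrawals.* The 26 patients beyond 74 are an allowance, not a forecast.

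It is also fair to say that patients who die or remain ventilated cannot give an IS under any plan.

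**Conclusion.** The concern holds in limited form. The rule removes randomised patients for post-randomisation events, at least one of which is by inference confined to the intervention arm, and nothing returns them to the primary test. The groups compared may therefore not be the groups randomised. Direction and size are unknown. The effect ranges from negligible at 2% withdrawn to a serious inflation of type I error at 20% with strong dependence, and both the rates and the correlations are assumptions. Comparable control losses would offset it. I rate this as should fix, below must-fix, with medium confidence.

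**What to change.** 1. Separate stopping the study ventilation, which remains a clinical decision and is unchanged, from leaving the study.
2. Record unmet ventilation goals or intolerance as non-adherence. Keep these patients in the 30-minute, 1-hour and 2-hour spirometry under the existing re-attempt rule of Section 10.0.
3. State that the primary test of mean change includes all randomised patients with a measured post-operative IS, in their assigned arm.
4. Report patients with no obtainable IS (for example after death, continued ventilation or ICU admission) by arm and reason, and state that bias from them can remain. A sensitivity analysis for them is optional, and its rule is the sponsor's choice.
5. Reconcile Sections 4.0 and 14.0. Intraoperative death appears only in 14.0, ICU admission is limited to immediate admission only in 14.0, and the ventilation reason is worded differently.

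The cost is protocol and SAP wording, a recorded reason for each event, and spirometry already scheduled for patients in PACU or on the floor. Spirometry in ICU is not scheduled now and is not required by this fix. The statistical price is the dilution in step 5 of the working: 2 to 12 percentage points of power at SD 300, or 3 to 14 at SD 350, over 5% to 20% non-adherence. In return, the test compares the arms as assigned among all patients who can be measured.
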